9. RISK ANALYSIS

Anticipated Risks

Edwards will monitor for safety which include those potentially associated with use of the devices and its components. There may be additional risks and discomforts that are not known at this time.

Any events associated with a commercially available study device (Fore-Sight Elite Tissue Oximetry Sensors) will be reported in accordance with the Medical Device Reporting (Complaints) regulation (21 CFR Part 803), while events associated with the investigational devices (remainder of devices in this study) will be reported under the IDE program (812.150).

Below is a list of general anticipated risks associated with the type of surgeries and procedures, which may be conducted as standard of care.

- Risks related to transplantation of donor organ:
 - Death
 - Explant of donor organ
 - Hemorrhage
 - Organ transplant failure
 - Respiratory Failure
 - Sepsis/Infection
- Risks related to other surgical or patient factors:
 - o 30-day mortality
 - Cardiac arrest
 - Cardiac arrhythmia
 - Hemorrhage
 - o Ileus
 - Nausea and vomiting
 - o Pneumonia
 - Prolonged Hospital length of stay
 - Prolonged ICU length of stay
 - Pulmonary embolism
 - Sepsis
 - Transfusion need
 - Wound infection

Below is a list of anticipated risks that may be associated with the use of Swan-Ganz thermodilution pulmonary artery catheter:

- Allergic reaction to latex
- Cardiac arrhythmias
- Complete heart block

THIS DOCUMENT CONTAINS CONFIDENTIAL AND PROPRIETARY INFORMATION OF EDWARDS LIFESCIENCES, LLC. IT MAY NOT BE REPRODUCED OR DISCLOSED WITHOUT PRIOR WRITTEN PERMISSION FROM EDWARDS LIFESCIENCES, LLC.

POGO Study

Study #2019-08

- Knotting
- Nitroglycerin absorption
- Perforation of the pulmonary artery
- Pneumothorax
- Pulmonary infarction
- Thrombocytopenia
- Thrombophlebitis
- Thrombosis
- Tricuspid and pulmonic valve damage
- Right bundle branch block
- Sepsis/Infection

Below is a list of anticipated risks that may be associated with the use of the FloTrac Sensor:

The vascular access obtained is standard clinical care for the adult population and the addition of the FloTrac sensor is and is not expected to impose any additional risk to the patient. There is no measurable increased infectious risk with the temporary use of the FloTrac sensor.

Below is a list of anticipated risks that may be associated with the use of the ClearSight finger cuff:

- Discoloration of digit distal to the cuff
- Discomfort where the cuff is applied
- Pain associated with inflation of the cuff
- Slight numbness of the fingertip

Below is a list of anticipated risks that may be associated with the use of ForeSight Elite Sensors:

- Allergic reaction to adhesive on sensors
- Skin irritation

POGO Study	
Study #2019-08	

Risk Management

The study devices have been tested to an established regimen of safety and performance testing and, with the exception of the ClearSight Module used in the HemoSphere platform, have been cleared by the US FDA in adults. The ClearSight technology has been cleared for use in adults with the EV1000 Monitor; however, it has not been cleared for use with the HemoSphere advanced monitoring platform.

The current risks identified for using these products do not outweigh the benefit the patient will receive. Furthermore, this study is:

- 1) Being conducted on patients who are already planned to receive an arterial line and a Swan Ganz catheter and the addition of FloTrac and ClearSight do not add to the invasiveness of the study,
- 2) Being conducted on patients who are already planned to receive thermodilutions
- 3) An observational study as opposed to an interventional study
- 4) Not relying on the data obtained from the FloTrac and ClearSight to treat patients

Collecting data does not introduce any new risks in relation to these products. Regarding the ClearSight Module used in the HemoSphere platform, thorough testing has been performed to show that this system functions as intended. As such collectively, the risks do not outweigh the benefits.

Benefits

There are no guaranteed benefits from a subject's participation in this study. However, the ForeSight Elite Sensors are cleared for pediatric use and provide the benefit of continually monitoring oxygen saturation of tissue with accuracy and precision. When desaturation of tissue occurs, the following may occur:

- Cognitive disfunction
- Extended time on mechanical ventilation
- Extra days spent in the hospital or intensive care unit (ICU)
- Increased post-operative nausea and vomiting

POGO Study]
Study #2019-08	

10. REPORTABLE EVENTS

Recording and Reporting of Adverse Events

The Investigator and/or Designee(s) will determine whether any adverse events (AEs) have occurred. An AE is defined as any untoward medical occurrence in a clinical Study of an Investigational Device regardless of the causal relationship of the problem with the device or, if applicable, other Study treatment or diagnostic product(s). Information for AEs with the study devices will be collected from the time a subject begins the study procedure and is exposed to Study products. AEs will also be collected during surgical intervention, post intervention, discharge and through the 30-day follow-up. AEs may be volunteered by subjects, clinicians, elicited from questioning by Investigator and/or Designee(s), or collected via observation. When a device or study related AE is suspected all available event information and will be provided to the Clinical Events Committee.

Once an AE/SAE/UADE is confirmed as such, event, date of onset, severity, duration, treatment (if required), resolution (or ongoing), assessment of seriousness, relationship to Study procedure and relationship to device will be recorded on the appropriate eCRF or SAE Report Form and submitted as necessary by the Investigator and/or Designee(s). Any suspected AEs related to the Investigational Device or Study procedure must be reported to the Sponsor or designee within 5 working days of first awareness of the event.

Recording and Reporting of Adverse Device Effects

An adverse device effect (ADE) is defined as an AE related to the use of an investigational medical device. This definition includes AEs resulting from insufficient or inadequate instructions for use, deployment, implantation, installation or operation, or any malfunction of the investigation device. It also includes any AE resulting from use error or from intentional misuse of the Investigational Device.

Causality of relationship to the Investigational Device will be judged by the Investigator, and reviewed independently by the Clinical Events Committee, as follows:

Not related:

• An event is clearly not and cannot be related to the Investigational Device. Reporting is not required per protocol unless the event was related to the Investigational Device or Study.

Possibly Related:

• A relationship may exist but could have been produced by another cause (e.g., treatment, condition).

Related:

• A relationship can be directly attributed to the use of the Investigational Device.

ADEs must be reported to the Sponsor or designee, within 24 hours of first awareness of the event. Notification should be done via email, fax, telephone or direct communication followed by direct entry of AE/SAE data into the eCRF. In addition, the Study site will report confirmed ADEs related to their IRB in accordance with the IRB's requirements. ADEs will also be reported to the FDA, as required.

THIS DOCUMENT CONTAINS CONFIDENTIAL AND PROPRIETARY INFORMATION OF EDWARDS LIFESCIENCES, LLC. IT MAY NOT BE REPRODUCED OR DISCLOSED WITHOUT PRIOR WRITTEN PERMISSION FROM EDWARDS LIFESCIENCES, LLC.

POGO Study	
Study #2019-08	

Recording and Reporting of Serious Adverse Event

A serious adverse event (SAE) is defined as an AE that results in any of the following outcomes: death, a life-threatening adverse event, inpatient hospitalization or prolongation of existing hospitalization, a persistent or significant disability/incapacity, or a congenital anomaly/birth defect.

Recording and Reporting of Serious Adverse Device Effects

A serious adverse device effect (SADE) is an ADE that has resulted in any of the consequences or characteristics of a SAE.

SADEs must be reported to the Sponsor or designee, within 24 hours of first awareness of the event. Notification should be done via email, fax, telephone or direct communication followed by direct entry of AE/SAE data into the eCRF. In addition, the Study site will report confirmed SADEs their IRB in accordance with the IRB's requirements. SADEs will also be reported to the FDA, as required.

Recording and Reporting of Unanticipated Adverse Device Events

Unanticipated adverse device effect (UADE) is defined in 21 CFR 812 as any serious adverse effect on health or safety or any life-threatening problem or death caused by, or associated with, a device, if that effect, problem, or death was not previously identified in nature, severity, or degree of incidence in the investigational plan or application (including supplementary plan or application), or any other unanticipated serious problem associated with a device that relates to the rights, safety, or welfare of subjects. In contrast, an anticipated adverse device effect is an effect which by its nature, incidence, severity, or outcome has been identified in the risk analysis report.

UADEs must be reported to the Sponsor or designee within 24 hours and submitted to the reviewing IRB as soon as possible, but in no event later than 10 working days after the Investigator first learns of the effect. All AEs related to the Investigational Device or Study will be reviewed by the Investigator and/or Designee(s) and Sponsor. These AEs will be followed until they are adequately resolved, explained by the Investigator and/or Designee(s), until subject has completed follow-up or been withdrawn from the Study.

POGO Study	
Study #2019-08	

Recording and Reporting of Deaths

Events resulting in death during the subject's enrollment in this Study are not expected to occur as a result of participation in the Study. In the event of subject death; however, every reasonable effort should be made to obtain a copy of the autopsy report and/or death summary. Information on the date and cause of death and its relationship to the Study device will be determined by the Investigator and/or Designee and recorded on the appropriate AE eCRF and submitted on an SAE Report Form as necessary.

Recording and Reporting of Adverse Events Associated with Commercial Components

Any adverse event associated with an FDA cleared component will be recorded as a device complaint and reported via the MDR program (21 CFR Part 803). Complaints will also be reported to the IRB in accordance with each IRB's requirements. Device complaints should be reported to the Sponsor as soon as the site becomes aware of the complaint.

Recording and Reporting of Pre-Existing Conditions

Pre-existing medical conditions and symptoms due to pre-existing medical conditions, surgery or admission to ICU will not be recorded as adverse events. The admission of a critically ill patient in the intensive care unit is commonly due to one or several serious medical conditions and/or a major surgery, which may cause changes and abnormalities of blood chemistry, diagnostic and physiological parameters. In the event there is a deterioration of a pre-existing medical condition or symptoms due to the use of the Study products or a Study related procedure, then the review of the event will be initiated, and an AE will be recorded if it meets the definition. Any events occurring prior to the study procedure will be recorded as medical history.

Reporting Adverse Events to the FDA

Confirmed UADEs will be evaluated by the Clinical Events Committee. The FDA, all participating principal investigators and their reviewing IRBs will be informed no later than 10 working days after Edwards Lifesciences or designee first becomes aware of the effect.

POGO Study	
Study #2019-08	

Reporting Adverse Events to the Responsible IRB

In accordance with applicable policies of the IRB, the Investigator will report, any observed or volunteered confirmed adverse event that is determined to be (1) unexpected; (2) related or possibly related to the research; and/or (3) involves increased or greater risk of harm to participant(s) or others than was previously known or approved by the IRB. AE reports will be submitted to the IRB in accordance with the IRB policies and procedures.

Confirmed UADEs will be evaluated and the reviewing IRB will be informed of the results of the Study no later than 10 working days after Edwards or when the designee first becomes aware of the effect.

POGO Study	
Study #2019-08	

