For PE, a sample size of n=60 will be used in the study design, after considering two pairwise comparisons between 2 devices with a reference device. In addition, after considering a 34.5% rejection rate for hemodynamic instability, 10% lost to follow-up rate, 102 evaluable subjects will be targeted. To account for the learning curve and 6 additional Roll-in Subjects will be enrolled, totaling 108 Subjects enrolled in the study.

Calculation of Cardiac Index (CI)

Adjusting cardiac output (CO) with study subject body surface area (BSA) results in the derivation of cardiac index (CI). This adjustment for body surface area, in the study pediatric population (12 to 18 years old), will result in a smaller bias and percent error between test device and reference device. The standard deviation estimate will also be smaller, at the same scale, thus, the sample size estimate decreases. Sample size estimates for bias and percent error for CI is detailed in the SAP.

THIS DOCUMENT CONTAINS CONFIDENTIAL AND PROPRIETARY INFORMATION OF EDWARDS LIFESCIENCES, LLC. IT MAY NOT BE REPRODUCED OR DISCLOSED WITHOUT PRIOR WRITTEN PERMISSION FROM EDWARDS LIFESCIENCES, LLC.

POGO Study		
Study #2019-08		

Primary Safety Endpoint

The primary safety endpoint is to assess all serious intraoperative and post-operative adverse events through 30 days, including serious device-related events.

Analysis Populations

All enrolled subjects with evaluable data will be included in the analysis of effectiveness endpoint, and all enrolled subjects will be included in the analysis of safety endpoint.

The analysis set is composed of all evaluable subjects with valid CO matched pair measurements from the target medical device system (FloTrac and ClearSight systems) and the reference medical device system (the Swan-Ganz thermodilution pulmonary artery catheter).

Evaluable subjects are those with non-rejected intermittent thermodilutions who have completed the 30-day telephone follow up period.

Analysis Methods

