9 ANALYSIS OF SAFETY

9.1 Adverse Events

[figure not shown]
The adverse events data will be summarized with frequency counts and percentages. The frequency distribution and percentage of adverse event related to a specific medical device will be presented. The primary safety endpoint will include summary of intraoperative and post-operative adverse events, discharge through 30 days followup, related or unrelated to the devices under study.

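### The protocol contradicts itself on capturing its primary safety endpoint: all serious events count, but the reporting rules let sites leave out those judged unrelated or due to surgery or ICU admission

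*Combined protocol and SAP*

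**What the plan says.** **Endpoint.** Protocol section 6 (*Primary Safety Endpoint*) reads: "The primary safety endpoint is to assess all serious intraoperative and post-operative adverse events through 30 days, including serious device-related events". The synopsis, protocol section 3 and SAP section 3 agree. Device-related events are thus a subset of the endpoint. SAP 9.1 describes the summary as covering events from "discharge through 30 days followup, related or unrelated to the devices under study". Protocol section 6 analyses safety in all enrolled subjects.

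**Text that captures events whatever their cause.** In protocol section 10, *Recording and Reporting of Adverse Events* defines an adverse event without regard to causality and extends collection through the 30-day follow-up. It has seriousness and relationship to procedure and device entered on the eCRF or SAE form. The section 8 schedule has adverse events recorded at procedure, discharge and day 30 with no relatedness condition. Section 11 gives the Clinical Events Committee (CEC) all adverse events to adjudicate.

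**Text that filters by cause.**
- Section 10, causality scale, category *Not related*: "Reporting is not required per protocol unless the event was related to the Investigational Device or Study".
- Section 10, on what reaches the CEC: "When a device or study related AE is suspected all available event information and will be provided to the Clinical Events Committee".
- Section 10, *Recording and Reporting of Serious Adverse Event*: a definition only, with no duty or timeline.
- Section 10, *Pre-Existing Conditions*: "symptoms due to pre-existing medical conditions, surgery or admission to ICU will not be recorded as adverse events". The exception is "deterioration of a pre-existing medical condition or symptoms due to the use of the Study products or a Study related procedure".

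**The concern.** The endpoint needs every serious event, but several of the rules that feed it depend on the investigator's causality judgement. A site that follows the waiver and the non-recording rule to the letter would leave out events that the endpoint counts. A site that follows the general collection paragraph would include them. Both could claim to be following the protocol.

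This endpoint is also what the Data Safety Monitoring Board (DSMB) assesses in closed session, and its advice on continuing the study rests on safety alone (section 11). An event left off the eCRF would not be there for the CEC to adjudicate or the board to weigh, and the omission always runs towards a lower event rate. The study is meant to support extending the devices' indications to patients aged 12 to 18, so the 30-day serious event count will be read as evidence in its own right.

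**Working it through.** The safety endpoint has no hypothesis, expected rate or sample size in the documents, so there is no stated figure to reproduce. The check is a comparison of texts, followed by arithmetic on assumed rates.

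**1. Follow one event through the rules.** Take a non-fatal serious event on day 5 that the investigator considers unrelated to device and study.

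| Step | Text that includes it | Text that leaves it out |
|---|---|---|
| Does the endpoint count it? | Protocol sections 3 and 6; SAP 3 and 9.1 | None |
| Is it an adverse event? | Section 10 definition, causality-neutral | None, unless attributed to a pre-existing condition, surgery or ICU admission |
| Is it recorded? | Section 10 general paragraph; section 8 schedule | *Pre-Existing Conditions* paragraph, for symptoms due to those three causes |
| Must it be reported? | No timed duty found | *Not related* waiver |
| Does it reach the CEC? | Section 11, all adverse events | Section 10, information sent when a relation is suspected |

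The timed duties to the sponsor are 5 working days for adverse events suspected to be related to the device or study procedure, and 24 hours for adverse device effects, serious adverse device effects and unanticipated adverse device effects. This event falls under none of them.

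**2. What is protected.** Deaths are recorded with their relationship to the device, and day 30 includes a mortality check. Study-related events stay outside the waiver. Deterioration due to study products or a study-related procedure stays recordable. The exposed group is therefore non-fatal serious events judged unrelated to both device and study, plus surgery- or ICU-related events.

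**3. Size, by formula.** Let N be subjects enrolled, r the share with a non-fatal serious event (one per subject, for simplicity), u the share of those events judged unrelated, and a the share of the unrelated events that arise where the waiver is applied to eCRF entry.

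Recorded events = N × r × (1 − u × a), so the fraction lost is u × a.

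N = 108 is the planned maximum (protocol section 4). The values of r, u and a are assumptions, because the documents give none. With a = 1:

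| r | Expected, 108 × r | u = 50% | u = 80% | u = 95% |
|---|---|---|---|---|
| 5% | 5.4 | 2.7 | 1.1 | 0.3 |
| 10% | 10.8 | 5.4 | 2.2 | 0.5 |
| 20% | 21.6 | 10.8 | 4.3 | 1.1 |

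Example: 108 × 0.10 × (1 − 0.80) = 2.16. With a = 0 (every site follows the general collection paragraph) nothing is lost. With a = 0.5, r = 10% and u = 80%, recorded events are 10.8 × (1 − 0.40) = 6.5.

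**4. Between-site effect.** Two sites with the same true rate of 10% and u = 80% would show 10% and 10% × 0.20 = 2% if one records every event and the other applies the waiver. With up to five sites, such a gap could be mistaken for a difference in safety.

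**The case against.** The strongest reply is that the protocol already captures these events. The definition ignores cause, collection runs to day 30, the schedule has no relatedness filter, and recording relatedness as a data field presupposes that unrelated events are entered. This stands, and it rules out a stronger reading that a reader might infer: that the endpoint cannot be computed, or is certain to be undercounted. The documents support only that it can be.

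Second, the waiver sits under *Adverse Device Effects*, close to the 24-hour notification rule, and section 10 elsewhere uses recording for eCRF entry and reporting for notification. The sentence may therefore mean only that no notification is due. That is a fair reading, but the text does not say so. Nor does it help with the *Pre-Existing Conditions* paragraph, which concerns recording itself.

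Third, that paragraph's heading and its rationale about patients' state on ICU admission suggest that it means baseline conditions. That is plausible. However, its wording is not limited to earlier surgery or an earlier ICU stay, and the endpoint counts intraoperative and post-operative events.

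Fourth, the CEC reviews causality independently and has all adverse events in its remit, and monitors check data against source records. A reader might infer that independent adjudication is bypassed altogether; the documents do not support that. What remains is that the CEC can adjudicate only what reaches it, and section 10 describes that flow only for suspected related events.

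Finally, the risk lists in section 9 carry no frequencies, and arrhythmia and sepsis appear on both the general and the Swan-Ganz lists. They cannot show what share of serious events would be called unrelated.

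**Conclusion.** The point holds as an internal contradiction. The endpoint and SAP 9.1 count serious events whatever their cause, and part of the protocol collects them that way. The *Not related* waiver, the CEC information rule, the missing duty for unrelated serious events and the surgery/ICU non-recording rule point the other way. Non-fatal serious events judged unrelated to device and study, and surgery- or ICU-related events, can be undercounted, and to different degrees at different sites.

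The direction is towards a lower rate. The size cannot be derived from the documents. Wherever the waiver governs eCRF entry, the loss equals the unrelated share of non-fatal serious events; where it does not, the waiver causes no loss. The counts in the tables rest on assumed rates and show only how the loss scales. It would also go too far to say that every unrelated serious event is at risk, since deaths are recorded regardless.

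The wording should still be corrected, because a site following the stated rules could omit events that the primary safety endpoint counts and the DSMB relies on.

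**What to change.** Reconcile protocol section 10 with the endpoint (protocol sections 3 and 6, SAP 3 and 9.1) and with the CEC remit in section 11:

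1. Limit the *Not related* waiver to non-serious events, or state that it concerns expedited notification only and not eCRF entry.
2. Limit the non-recording rule under *Pre-Existing Conditions* to conditions present before the procedure and unchanged since.
3. State under *Serious Adverse Event* that every serious event from first device exposure through day 30 is entered on the eCRF and sent to the CEC, whatever the investigator's causality call. Align the sentence on what the CEC receives.
4. Align SAP 9.1, whose sentence on the primary safety endpoint omits the word serious.

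If the sponsor does not want to collect unrelated serious events, the alternative is to restate the endpoint as related serious events only, in both documents.

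The cost is a wording amendment plus a modest number of extra eCRF entries and adjudications. Events not captured while the study runs may be hard to recover later.

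### The serious adverse event definition has no intervention criterion, so some treated catheter complications can fall outside the serious-only safety endpoint; serious events and deaths judged unrelated have no sponsor-notification time

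*Combined protocol and SAP*

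**What the plan says.** **Definition.** Protocol section 10 (Recording and Reporting of Serious Adverse Event) limits seriousness to five kinds of outcome: "death, a life-threatening adverse event, inpatient hospitalization or prolongation of existing hospitalization, a persistent or significant disability/incapacity, or a congenital anomaly/birth defect". The next subsection carries the list over to device effects: "A serious adverse device effect (SADE) is an ADE that has resulted in any of the consequences or characteristics of a SAE". Neither the protocol nor the SAP adds a criterion based on intervention or medical importance.

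**Endpoint.** Protocol section 6 states: "The primary safety endpoint is to assess all serious intraoperative and post-operative adverse events through 30 days, including serious device-related events". The Synopsis, protocol section 3 and SAP section 3 agree. SAP 9.1, which specifies the analysis, omits the seriousness limit: "The primary safety endpoint will include summary of intraoperative and post-operative adverse events, discharge through 30 days followup", whether or not related to the devices. SAP 9.2 tabulates deaths and other serious events.

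**Expected complications.** Protocol section 9 lists the anticipated Swan-Ganz risks. They include knotting, pneumothorax, complete heart block, pulmonary artery perforation and valve damage.

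**Reporting times.** Section 10 sets times for device effects and for suspected device- or procedure-related events. It sets none for serious events as such. For deaths it says only that details are "recorded on the appropriate AE eCRF and submitted on an SAE Report Form as necessary". Under the causality categories, it says events judged not related to the device need not be reported unless they were related to the device or the study.

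**The concern.** The Swan-Ganz catheter is investigational in this age group, and the study is meant to support a pediatric indication for it. The safety endpoint should therefore capture the harms most specific to it. Under a list with no intervention criterion, a complication can escape the serious count precisely because it was corrected promptly. Assessing the primary safety endpoint is one of the DSMB's closed-session tasks (protocol section 11), so the classification also affects oversight.

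The second strand is timing. Suspension for suspected unacceptable risk (protocol section 8) presupposes that the sponsor learns of serious events soon, including those that the site first attributes to something else. If the reporting times depend on attribution, the investigator's initial causality judgement decides how quickly anyone else can question it.

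**Working it through.** No arithmetic reproduces this point: the plan states no safety rate, threshold, hypothesis or safety sample size. The check sets the passages side by side.

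**1. One event against the definition.** Take a pneumothorax during catheterization, treated at once.

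| Criterion in section 10 | Met? |
|---|---|
| Death | No |
| Life-threatening | Only if judged so; suppose not |
| Hospitalization or longer stay | Only if it causes or prolongs one; suppose not |
| Persistent or significant disability | Suppose not |
| Congenital anomaly | Not applicable |

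None is met, so the event is non-serious. An intervention criterion would make it serious if the treatment was needed to prevent one of these outcomes. The same reasoning applies to a knotted catheter resolved during the procedure.

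**2. Where that event is counted.**

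| Place | Included? |
|---|---|
| Primary safety endpoint in the Synopsis, protocol sections 3 and 6, SAP section 3 | No |
| Deaths and serious events, SAP 9.2 | No |
| All-event summary under the primary safety endpoint, SAP 9.1 | Yes |
| Device-specific table, SAP 9.1 | Yes, if attributed to a device |

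So whether the event belongs to the primary safety endpoint depends on which section is read.

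**3. Time to sponsor.**

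| Event | Time stated in section 10 |
|---|---|
| Adverse device effect, serious or not | 24 hours |
| Serious adverse device effect | 24 hours |
| Unanticipated adverse device effect | 24 hours |
| Suspected device- or procedure-related event | 5 working days |
| Serious event judged unrelated to device or procedure | None |
| Death judged unrelated to device or procedure | None |

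For the last two rows the only limit is the general eCRF timing in protocol section 12 (Source Documents): 24 hours recommended and 10 working days at most. A non-serious finger-cuff effect judged device-related thus has a firm 24-hour limit, and an unrelated death does not.

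**4. The waiver for not-related events.** It cannot be squared with an endpoint covering all serious events, or with SAP 9.1, which includes unrelated events. A site following it literally could omit data that the endpoint needs.

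**5. Scale.** Each reclassified subject moves the serious-event percentage by 1/108 = 0.93 points if all 108 planned subjects are the denominator, or by 1/102 = 0.98 points for the 102 pivotal subjects. How many such events to expect cannot be derived from the documents.

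**The case against.** The strongest reply is that little is lost. SAP 9.1 summarises all adverse events under the primary safety endpoint and tabulates those related to each device. Treatment is recorded for every confirmed event (protocol section 10), so events that needed intervention can be identified. The CEC adjudicates every event as serious or non-serious. A complication judged device-related reaches the sponsor within 24 hours regardless of seriousness, so the missing criterion does not delay any suspension. No prespecified decision depends on the serious-event rate.

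Most of this stands and limits the point to classification. It does not remove it. The endpoint is worded as serious-only in four places. The protocol gives the CEC no criterion beyond the list, and its charter is not among the documents. The 24-hour route depends on the event being judged device-related, so it does nothing for serious events and deaths judged unrelated.

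A reader might infer more: that Swan-Ganz complications handled on the spot generally count as non-serious and disappear from the safety results. The documents do not support that. A complication judged life-threatening, as pulmonary artery perforation or complete heart block could be, is already serious however well it was treated. So is one that prolongs a stay. Nor do the documents say that subjects are inpatients: they refer to a planned catheterization, and for a day case a resulting admission would itself make the event serious. Finally, nothing in the documents shows that the extra criterion is mandatory, and no such claim is made here.

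**Conclusion.** The point holds in a narrow form. The definition leaves a gap for complications that needed intervention, were not judged life-threatening, neither caused nor prolonged hospitalization, and left no disability. These can be absent from the endpoint as four sections define it and from the serious-event table, but not from the all-event summary. The serious-only wording and SAP 9.1 need reconciling in any case.

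The reporting gap is separate and rests on the text alone: serious events and deaths judged unrelated have no sponsor-notification time, and the waiver for not-related events contradicts the endpoint.

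The size is unknown. The classification gap rests on two assumptions: that such events occur, and that the unseen CEC charter adds no seriousness criterion. The case for change is that it improves ascertainment and oversight cheaply; it does not show that any planned conclusion would be wrong.

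**What to change.** - Add to the serious adverse event definition: *or required medical or surgical intervention to prevent any of the above outcomes*. The serious adverse device effect definition then inherits it. Carry the clause into the SAE form and the CEC charter, and have the CEC apply it when adjudicating seriousness.
- Put all serious adverse events and all deaths, whatever their attribution, on the 24-hour sponsor notification already used for serious device effects.
- Delete the sentence waiving reporting of not-related events, or reconcile it with the endpoint.
- State once whether the primary safety endpoint is serious events or all events, and align the Synopsis, protocol sections 3 and 6, SAP section 3 and SAP 9.1.

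The cost is a short amendment, with a slightly higher reported serious-event rate and a few more expedited reports. No new data field is needed, because treatment is already recorded for each event.
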